9.1. Possible Expected Adverse Events

Minimal adverse events can be expected during or after the LEGO®-based therapy sessions, and these will be reduced by 'club rules' (e.g. no LEGO® in the mouth) and monitoring by the interventionist who will be trained to deal with the child's distress. These adverse events may include:

• Choking on or swallowing LEGO®;

- Emotional distress or social anxiety that could lead to behaviours such as:
 - destruction of property (children may smash LEGO® models, throw furniture or break other items);
 - verbal abuse;
 - physical violence (children with ASD may express frustration/sadness/anxiety through hitting/biting/aggression);
 - running away to escape the situation.

SAEs considered related (to the intervention) and unexpected (i.e. not listed above) will be reported to the sponsor, the DMEC and the TSC within 15 working days of the CTRU being informed of the event and the TSC and DMEC will review all other SAEs at the next scheduled meeting.

10. Statistics and Data Analysis

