5.1. Internal Pilot

The RCT will contain a ten month internal pilot. At the end of this period, the trial team will report to the NIHR on whether criteria for stopping have been met and whether the trial should continue. Sheffield CTRU will aggregate study data to assess feasibility of the research. Stop/Go criteria (see section 10.1) will be based on the feasibility of recruitment, retention and safety outcomes. We anticipate a recruitment rate of 12 children (six schools) per month. At ten months, we would have expected to recruit 120 children, and we will include a stopping criterion

of 75% of the recruitment target n=90. At this point, one third of the recruited participants would have reached the primary endpoint (n=40) and we would expect that 70% of the outcome measures will have been completed (n=28). As the trial exposes children with autism to a novel social situation, a Data Monitoring and Ethics Committee (DMEC) will review the data at the end of the pilot and throughout the trial for safety (see section 9.1). If there is evidence of harm due to the interventions or measures the trial may be stopped.

6. Eligibility Criteria

A number of inclusion and exclusion criteria must be met before a participant can be included in the trial. As I-SOCIALISE is a pragmatic trial, very few exclusion criteria will be applied. A detailed overview of the inclusion and exclusion criteria for the I-SOCIALISE trial is below.

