8.4.5. English as an additional language

We do not have funding for translators or to develop the study materials in other languages and so we will not be able to recruit where parents/guardians cannot understand written English, as they will not be able to provide fully informed consent or complete the study measures. Existing school services will be used for children with language and comprehension difficulties where appropriate.

9. Monitoring of Adverse Events

Possible harm as a result of the study is expected to be minimal but will be monitored according the Sheffield CTRU SOPs.

- 1. Questions relating to Adverse Events (AEs) will be used to record any untoward occurrence affecting the participant after each LEGO®-based therapy session by the interventionist and at the 20 week follow-up conducted by the research assistant.
- 2. Teachers and parents will be asked if they believe there have been any untoward events (above the child's usual behaviour) at the 20 week time point.
- 3. All AEs will be assessed for seriousness, and will be recorded as a Serious Adverse Event (SAE) if it;
 - Results in death
 - Is life-threatening
 - Requires hospitalisation or prolongation of existing inpatients hospitalisation
 - Results in persistent or significant disability or incapacity
- 4. The occurrence of adverse events during the trial will be monitored by the DMEC and the TSC.

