11.3. Archiving

Study documentation and data will be archived at a suitable time following database lock. All essential study documents will be retained as part of the trial master file and individual site files. After notification of study completion, all documentation and study data will be stored securely for five years and will be accessible for inspections and audits.

12. Monitoring, Audit and Inspection

Trial monitoring procedures and site monitoring will be undertaken at a level appropriate to a risk assessment performed by the Sponsor and the CTRU according to CTRU SOPs, and significant findings will be presented to the appropriate oversight committee.

Three committees will be established to govern the conduct of this study:

- A Trial Steering Committee (TSC).
- An independent Data Monitoring and Ethics Committee (DMEC).

• A Trial Management Group (TMG).

These committees will function in accordance with Sheffield CTRU SOPs. The TSC will consist of an independent chair, an independent subject specialist, an independent clinical academic, an independent statistician and a PPI representative. The DMEC will consist of an independent chair, an independent statistician, and another independent member experienced in research with children and families. The TSC and DMEC will meet approximately every 6 months from the start of the trial. The TMG will comprise the co-applicants, members of the trial team (including the data manager), PPI representatives, and the two trial managers who will be jointly supervised by the CI, and the director of the Sheffield CTRU. Meeting attendance of the co-applicants and trial team will depend on the agenda and relevance to their role.

13 Ethical and Regulatory Considerations

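### Section 9.1 lists choking on or swallowing LEGO as expected with no severity limit, so read literally a related serious case misses the 15-working-day report

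*Protocol*

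**What the plan says.** Four parts of the protocol bear on this point.

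- **Seriousness (section 9).** An adverse event is an SAE if, among other criteria, it "Results in death" or is life-threatening. The section also says that harm will be monitored under the Sheffield CTRU SOPs and that the DMEC and TSC will monitor adverse events during the trial.
- **The expected list (section 9.1).** The lead-in reads "Minimal adverse events can be expected during or after the LEGO®-based therapy sessions". The first item is "Choking on or swallowing LEGO". The other items are distress or social anxiety and the behaviours it may lead to, including physical violence and running away. No item carries a severity grade.
- **The reporting rule (section 9.1).** "SAEs considered related (to the intervention) and unexpected (i.e. not listed above) will be reported to the sponsor". Both oversight committees receive the same report, and the limit is 15 working days, counted from when the CTRU learns of the event. A second route covers what remains: "the TSC and DMEC will review all other SAEs at the next scheduled meeting". The sponsor is not named for this second route.
- **Meeting frequency (section 12).** "The TSC and DMEC will meet approximately every 6 months from the start of the trial".

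Section 5.1 adds that the DMEC reviews data for safety at the end of the pilot and throughout the trial, points to section 9.1 for this, and says: "If there is evidence of harm due to the interventions or measures the trial may be stopped".

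**The concern.** A type of event can be foreseeable while its serious form is not. Section 9.1 does not separate the two: an event type on the list counts as expected whatever its outcome. The lead-in points the other way, since it foresees only minimal events, and section 2.1 considers direct harm unlikely. On the protocol's own account a life-threatening choking is not something to be expected, yet the operative definition treats it as expected.

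The consequence concerns oversight. Section 5.1 allows the trial to be stopped for harm and relies on section 9.1 for the safety review. Under the literal rule, a related serious choking has no stated deadline for reaching the sponsor, and the only stated point at which the TSC and DMEC consider it is their next scheduled meeting. Sessions in other schools could continue in the meantime. The interval between meetings, about 26 weeks, is longer than a full course of about 12 weekly sessions (section 8.1).

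**Working it through.** No sample size, power or error rate is involved. The check traces the reporting rule for one case and then compares the two time limits.

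**Tracing the rule for a related, fatal or life-threatening choking on LEGO**

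| Test | Source | Result |
|---|---|---|
| Serious? | Section 9, death and life-threatening criteria | Yes |
| Related to the intervention? | Section 9.1 | Yes (by assumption in this case) |
| Unexpected, meaning absent from the list? | Section 9.1, first list item | No: the type is listed, with no severity limit |
| Both related and unexpected? | Section 9.1 reporting rule | No |
| Route | Section 9.1, rule for other SAEs | Next scheduled TSC and DMEC meeting |

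No other section of the protocol expedites a fatal, life-threatening or related SAE whose type is on the list.

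**Comparing the times**

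- Expedited route: 15 working days / 5 per week × 7 = 21 calendar days at most, counted from when the CTRU is informed.
- Scheduled route: meetings about every 6 months, 365 / 2 ≈ 183 days apart, so the wait is 0 to about 183 days.
- Mean wait, assuming that events fall evenly between meetings: 183 / 2 ≈ 91 days.
- Largest difference between the two limits: 183 − 21 = 162 days.

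Six months is thus the approximate maximum, not the typical wait. If a meeting happens to fall within 21 days, the scheduled route is no slower.

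**The other listed items**

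Violence and running away are listed as behaviours that distress may lead to. An injury that follows, such as a fracture, is not itself on the list. Such an SAE could be classed under the behaviour (listed, so not expedited) or under the injury (unlisted, so expedited). The text does not settle which. For choking or swallowing, the listed term is itself the event, so the literal result is clear.

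**The case against.** **The lead-in limits the list.** The list can be read as giving examples of minimal events only, so that a fatal choking is not on it, is unexpected, and is due within 15 working days. This is a reasonable reading of the intent, and a reader should not infer that the protocol deliberately withholds fatal events from prompt reporting. But the definition inside the reporting rule turns only on presence in the list and does not mention severity. Two readings are open, and the literal one gives the worse result.

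**The CTRU SOPs may be faster.** Section 9 places monitoring under SOPs that are not shown. This stands as a limit on the claim: an actual delay cannot be asserted. It does not remove the defect, because the protocol states an explicit rule and mentions no stricter procedure that overrides it.

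**Review is not first notice.** Section 9.1 says when the committees review other SAEs, not when they first hear of them. Section 9 has them monitor adverse events, and section 7.6 lets the DMEC ask for unblinded data if it is concerned. So a reader might infer that the committees would certainly learn late, and the text does not say that. Equally, none of these provisions sets a deadline for notice, and a request under section 7.6 presupposes that the DMEC already has a concern.

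**Such events are unlikely.** Section 2.1 describes close supervision, and section 9.1 adds club rules against putting LEGO in the mouth. This stands, and it bears on frequency. It also means that the remedy adds very little work.

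**Conclusion.** The point holds as a defect in the wording of section 9.1. Read literally, a related SAE of choking on or swallowing LEGO, even if fatal or life-threatening, is outside the 15-working-day report to the sponsor, DMEC and TSC. It waits 0 to about 6 months for a scheduled meeting, and section 9.1 names no report to the sponsor. This rests on taking the definition of unexpected at its word and on the SOPs adding nothing faster.

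Three stronger inferences are not supported:

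- That every serious event linked to a listed item is exempt. Injuries after violence or running away are not themselves listed, so their route is unclear.
- That the usual delay is six months. That is the approximate maximum; the mean is about 3 months if events are evenly spread.
- That the listed items are the main ways in which the intervention could seriously hurt a child, or the events most likely to justify stopping. The protocol does not rank harms in that way.

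The wording should be corrected because it governs information that the oversight committees may need for a stopping decision. Design and analysis are unaffected.

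**What to change.** Reconcile the lead-in, the list and the reporting rule in section 9.1 by adding one sentence: listed events count as expected only when they are non-serious. Any SAE judged related to the intervention would then be reported to the sponsor, DMEC and TSC within the existing 15 working days, whether or not its type is listed. This also settles the unclear cases of injury after violence or running away. SAEs judged unrelated would continue to go to the next scheduled meeting.

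Align the CTRU safety SOP with the new sentence. If the SOP already requires faster notice, section 9.1 should say so.

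The cost is a short protocol amendment and a few extra expedited reports at most.

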10.1. Sample size calculation

The sample size calculation is based on the (Reichow et al., 2012) Cochrane review which reported on five studies that examined the effects of social skills groups on social competence. This context was selected as the best indicator of realistic clinical effectiveness on the basis that if the proposed intervention was to be viable it needs to be at least as effective as running a social skills group in school. Of the five studies included in this review, four were RCTs and reported standardised measures of social competence which could be synthesised through meta-analysis techniques. The weighted mean standardised difference in social competence between group treatment and services as usual was 0.47 (95% confidence interval from 0.16 to 0.78). Reichow, et al., (2012) argued that this average effect size of almost 0.5 of an SD corresponds to a clinically significant change, 'to put these gains in more concrete terms, if measuring everyday socials skills using the Vineland (Sparrow 2005) for example an average participant from these studies would increase their repertoire of social skills from 123 to 147 after participating in the social skills group which is a clinically significant increase'. Calculations using this standardised effect size of 0.47, 90% power and 5% two sided significance results in a sample size of 97 participants per condition or 194 participants in total. Attrition rates varied between 0% and 16% for the studies included in the (Reichow et al., 2012) Cochrane review. As such, a conservative estimate of 16% inflates the sample to a final size of 116 participants per condition or 232 in total. To account for trainer/school effects and a cluster size of approximately 4 (2 participants per therapy group and 2 therapy groups per school) (ICC=0.01), based on the findings of the ASSSIST feasibility study conducted in the York area (Wright et al., 2016) this figure was further inflated and rounded up to 120 participants per condition or 240 in total. We anticipate recruitment of 12 per month across all sites and have a retention rate of 84% at 20 week follow-up. The pilot period will run for 10 months, at which point we expect to have recruited n=120 of which one third (n=40) will have reached the primary endpoint. Stop/Go criteria based on 75% of recruitment target (n=90) and 70% of the primary outcome measures (n=28) will be used to assess feasibility of continuing the trial.

10.2. General Approach to Data Analysis

As this trial is a pragmatic cluster RCT, data will be analysed and reported according to both RCT and cluster RCT CONSORT guidelines (Schulz, Altman, & Moher, 2010; Campbell,

Piaggio, Elbourne & Altman, 2012). Baseline demographic (e.g. age, gender) and outcome measures (e.g. SDQ) will be assessed for comparability between groups.

We will use ITT analysis for all outcome measures, including those who withdraw from the treatment but complete outcome measures. This is the most appropriate form of analysis for a pragmatic trial as it maximises the external validity of the data despite the danger of dilution bias (Torgerson & Torgerson, 2008). Hence we can evaluate the evidence that the intervention has an effect on the social competence and perceived social isolation of children with ASD within a school setting. Per protocol analysis will include participants who have received 6 or more sessions of LEGO®-based therapy.

10.3. Primary and secondary outcomes analysis

The primary outcome will be the associated teacher reported social skills subscale of the SSIS measured at 20 weeks after randomisation. The SSIS will also be completed at 52 weeks post randomisation. The social skills subscale of the SSIS is a summated score which we will treat as a continuous variable. All measures will be compared between the two treatment groups using a generalised linear mixed model to account for clustering. We will include the following variables as covariates: age, sex, baseline social skills subscale of the SSIS, participant group (random effect), school (random effect), number of eligible children (stratification variable: less than or equal to 6 or more than 6) and school level (stratification variable: primary or secondary school). An unadjusted analysis (difference between group means and 95% confidence intervals) will be reported alongside the adjusted analysis. The significance level will be set at 5% for testing the primary outcome.

The secondary outcome variables will also be treated as continuous variables and analysed (adjusting for baseline score, age, sex, school level (stratification variable), number of eligible children (stratification variable), participant group (random effect), and school (random effect)) using the generalised linear mixed model framework.

10.4. Missing or spurious data

We anticipate some attrition so missing data may be an issue. Case and item missing data will be examined and multiple imputation methods will be used to reduce bias due to any missing responses in the analyses. Where appropriate, modelling methods that generate robust standard errors in the presence of missing data will be considered.

10.5. Fidelity Analysis

The fidelity evaluation will examine the extent to which the components of the intervention (LEGO®-based therapy) are delivered as planned, and the accommodations required by the host service/system to ensure this. Facilitators' adherence to core components will be assessed using standard, weekly completed checklists developed by the research team to assess implementation fidelity, which comprises indices for adherence, dose/exposure, quality of delivery and participant responsiveness. This will correspond with the components set out in the respective manual.

Adherence to an average of 80% of the content will be considered acceptable fidelity. We will produce descriptive statistics on all completed fidelity checklists.

We will also record 72 (10%) of the LEGO®-based therapy sessions across the study and sample according to school level (primary/secondary) and sociodemographic variables. We will aim to involve 24 schools with three sessions per school recorded (one of the first four sessions, one of the second four sessions and one of the last four sessions). However in the event that there are fewer schools consenting to be video recorded,(recordings are done only if there is consent from each member of the group) we may need to increase the number of sessions recorded per school to achieve our target of 72 (10%) of the sessions. To assess the fidelity of the intervention, the video sessions will be reviewed by two independent observers and the inter-rater reliability calculated.

10.6. Economic Analysis

Using a UK NHS and education perspective, the economic evaluation will take the form of a within-trial cost-effectiveness analysis that will determine the incremental cost per unit of outcome measure for LEGO®-based therapy compared with usual support in children with ASD. Health outcomes will be measured in terms of quality-adjusted life years (QALYs) using EQ-5D-Y proxy as a health descriptor measure [the preferred instrument in the NICE reference case]. The domains of EQ-5D proxy (3L version) will then be valued using UK population tariff to provide utility scores at multiple time points. A secondary analysis will be conducted using the Child Health Utility 9D (CHU-9D) measure to estimate QALYs based on the UK population tariff (Stevens, 2011).

Resource use data will be collected using a bespoke questionnaire that will capture data on the following: (1) use of community health services, including appointments with general practitioner, nurse, child development centre, walk-in-centre, social worker, family support worker, educational psychologist, educational welfare officer and school and college nurse; (2) mental health services, including psychiatrist, psychologist, CAMHS therapist, mental health nurse, family therapist, GP counselling, school counsellor and any privately paid mental health services; (3) hospital visits, including outpatient visits, inpatient admissions, accidents and emergency visits and urgent care centre visits; (4) school-based interventions/support provided by teachers; (5) cost of the LEGO-based therapy sessions; and (6) cost of travel for therapy sessions. Finally, data on costs and outcomes will be analysed together using an incremental cost-effectiveness analysis which evaluates differences in costs and effects against a range of willingness-pay thresholds of the decision maker for a one unit gain in QALY.

10.7. Qualitative Analysis

In addition to the planned quantitative analysis, the proposed research will conduct a qualitative investigation to examine the acceptability of LEGO®-based therapy.

We will invite a sub-sample of the interventionist teachers/ TAs to participate in interviews and use a purposive sample of 20% of the interventionists across school types (primary/secondary and sociodemographic variables) post-intervention (n=12). The interviews will be undertaken by a member of the research team and will be unblinded to trial allocation. Normalisation Process Theory (NPT) (May et al., 2007) will be used throughout the interviews to guide data collection and to frame the analysis to understand how easy it is to implement LEGO®-based therapy into routine practice. All interviews will be recorded and transcribed verbatim. The framework

analysis approach (Spencer et al., 2003) will be used to structure and explore the interview data, and NVivo software will be used to support this process.

Data coding will be undertaken independently by two trained researchers. We will additionally train a PPI representative coder to work alongside these researchers, and to ensure coding takes account of potential differences in perspective. Coders will meet regularly to develop a shared coding manual and to ensure that all emerging codes remain grounded in original data. An Excel spread sheet will be developed which will incorporate preliminary framework themes as column headings and the demographic information related to participants who provided data under each theme. As the constant comparison of new data occurs and the coding team's understandings of the themes under consideration develop, the framework will be amended and re-shaped to enable the introduction of new codes and/or the deletion of redundant, similar or otherwise compromised codes. In this way, a final framework will be achieved that is considered representative of the entire dataset. The final coding manuals, with example entries, will be presented to the TMG and TSC to confirm its validity, coherence and conceptual relevance. Co-applicant [name] from the University of Sheffield will supervise the qualitative study and analysis.

The key ethical issues for the qualitative aspect of the study include confidentiality, participant anonymity, and informed consent to participate in research. Whilst the risk is small, there is a small possibility that participants might become distressed by disclosures about their own experiences during interviews and there may be disclosures relating to professional practice. A distress policy will be developed in consultation with the advisory team and a clinical lead will be identified from whom advice and guidance may be sought should the need arise. The information sheets will provide potential participants with information about the study, including the potential benefits and risks of taking part and information on anonymity and confidentiality.

11. Data Handling

